5.2. Handling of missing data and drop-outs

Missing data, missed training sessions or discontinuation are recorded on the CRF. Data from patients who drop out are achieved and stored. Drop-outs are not replaced by recruitment of new participant. If consent is withdrawn, the data already collected are included in the analysis for scientific and safety reasons. These are only anonymised after the analysis (Art. 9 ClinO).

6 REGULATORY ASPECTS AND SAFETY

6.1 Local regulations / Declaration of Helsinki

This study is conducted in compliance with the protocol, the current version of the Declaration of Helsinki, the ICH-GCP, the HRA as well as other locally relevant legal and regulatory requirements.

6.2 (Serious) Adverse Events and notification of safety and protective measures

An Adverse Event (AE) is any untoward medical occurrence in a patient or a clinical investigation subject which does not necessarily have a causal relationship with the trial procedure. An AE can

therefore be any unfavourable or unintended finding, symptom, or disease temporally associated with a trial procedure, whether or not related to it.

A **Serious Adverse Event (SAE)** (ClinO, Art. 63) is any untoward medical occurrence that

- Results in death or is life-threatening,
- Requires in-patient hospitalisation or prolongation of existing hospitalisation,
- Results in persistent or significant disability or incapacity, or
- Causes a congenital anomaly or birth defect

Both Investigator and Sponsor-Investigator make a causality assessment of the event to the trial intervention, (see table below based on the terms given in ICH E2A guidelines). Any event assessed as possibly, probably or definitely related is classified as related to the trial intervention.

Relationship	Description
Definitely	Temporal relationship Improvement after dechallenge* Recurrence after rechallenge (or other proof of drug cause)
Probably	Temporal relationship Improvement after dechallenge No other cause evident
Possibly	Temporal relationship Other cause possible
Unlikely	Any assessable reaction that does not fulfil the above conditions
Not related	Causal relationship can be ruled out

*Improvement after dechallenge only taken into consideration, if applicable to reaction

Both Investigator and Sponsor-Investigator make a severity assessment of the event as mild, moderate or severe. Mild means the complication is tolerable, moderate means it interferes with daily activities and severe means it renders daily activities impossible.

No (serious) Adverse Events are expected.

Reporting of SAEs (see ClinO, Art. 63)

All SAEs are documented and reported immediately (within a maximum of 24 hours) to the Sponsor-Investigator of the study.

If it cannot be excluded that the SAE occurring in Switzerland is attributable to the intervention under investigation, the Investigator reports it to the Ethics Committee via BASEC within 15 days.

Follow up of (Serious) Adverse Events

Not applicable, no SAE are expected in this study design.

Notification of safety and protective measures (see ClinO, Art 62, b)

If immediate safety and protective measures have to be taken during the conduct of the study, the investigator notifies the Ethics committee of these measures, and of the circumstances necessitating them, within 7 days.

6.3 (Periodic) safety reporting

An annual safety report (ASR) is submitted once a year to the local Ethics Committee by the Investigator (ClinO, Art. 43 Abs 1).

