7.2 Risk-benefit assessment

There are no health risks associated with participating in this study. The ILEX machine is CE-certified and based on equipment that has already been tested. The product is used in accordance with the instructions for use. The training sessions take place at low load and with a slow increase in load, which means that there is a negligible risk of injury. It is possible that fatigue of the back muscles or slight muscle soreness limited to the back may occur as a result of the training.

The use of diathermy therapies has been common practice for two decades. Treatment with the diathermy device is safe and most people find it very pleasant. Very sensitive skin may experience temporary redness and/or tingling. The tecar device is CE-certified and is used in accordance with the instructions for use.

Participation in the study does not result in any direct benefits for the test person. Ideally, the test participants improve the strength of the back extension muscles. The results of the study will help future people with back pain to receive effective treatment.

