9 MONITORING AND REGISTRATION

The monitoring will be done by [name] [name] from the institution THIM – Die internationale Hochschule für Physiotherapie, [name].

[name] will ensure that trial is conducted and documented properly by carrying out the following activities when relevant and necessary to the trial:

- Verifying that the investigator has adequate qualifications and resources and remain adequate throughout the trial period, that facilities, including laboratories, equipment and staff, are adequate to safety and properly conduct the trial and remain adequate throughout the trial period.
- Verifying for the study interventions:
 - o That the intervention conditions are acceptable.
 - o That the study interventions are supplied only to subjects who are eligible to receive it.
 - o That subjects are provided with necessary instructions on the study interventions.
- Verifying that the investigator follows the approved protocol and all approved amendments, if any.
- Verifying that written informed consent was obtained before each subject participation in the trial.
- Ensuring that the investigator and the investigator's trial staff are adequately informed about the trial.
- Verifying that the investigator is enrolling only eligible subjects.
- Reporting the subject recruitment rate.
- Verifying that the investigator provides all the required reports, notifications, applications, and submissions, and that these documents are accurate, complete, timely, legible, dated, and identify the trial.
- Adverse events, concomitant medications and intercurrent illnesses are reported in accordance with the protocol on the CRFs
- Visits that the subjects fail to make, tests that are not conducted and examinations that are not performed are clearly reported as such on the CRFs.
- All withdrawals and dropouts of enrolled subjects from the trial are reported and explained on the CRFs.

This study will be registered on the Swiss National Clinical Trial Portal.

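### Section 6.2 drops follow-up of all adverse events for a reason that covers only serious ones, and so conflicts with its own causality grading; its expectation of no events conflicts with section 7.2

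*Combined protocol and SAP*

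**What the plan says.** The relevant text is in four places.

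- **Section 6.2, definition and grading.** An adverse event includes "any unfavourable or unintended finding, symptom, or disease temporally associated with a trial procedure, whether or not related to it". The investigator and the sponsor-investigator both grade severity and causality. In the causality table, the two highest grades use improvement after dechallenge, where that applies to the reaction. The section then states "No (serious) Adverse Events are expected".
- **Section 6.2, reporting and follow-up.** Serious events are documented and go to the sponsor-investigator within 24 hours. They go to the Ethics Committee within 15 days if a link to the intervention cannot be excluded. The next heading is "Follow up of (Serious) Adverse Events", and its entire content is "Not applicable, no SAE are expected in this study design".
- **Section 7.2.** It opens with "There are no health risks associated with participating in this study". On training it says "It is possible that fatigue of the back muscles or slight muscle soreness limited to the back may occur as a result of the training". On diathermy it says "Very sensitive skin may experience temporary redness and/or tingling".
- **Section 9.** The monitor's checklist includes: "Adverse events, concomitant medications and intercurrent illnesses are reported in accordance with the protocol on the CRFs".

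The list of CRF content in section 8.2 and the schedule in Appendix 1 name no adverse event item. Section 5.1 plans no listing or table of adverse events.

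**The concern.** A protocol that says nothing about follow-up leaves room for ordinary good practice. This one states that follow-up does not apply. Staff who follow the text could grade an event, enter it on the CRF and stop there, with no obligation to record whether or when it resolved.

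Two things are at stake. First, healthy volunteers who are told to expect no direct benefit could have a reaction whose course is never documented. Second, the sponsor would have incomplete information for the causality grades, for the annual safety report in section 6.3, and for the provision in section 6.7 that allows early termination on evidence of harm.

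**Working it through.** No figure in the plan is at issue, so the check compares the text with itself.

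**1. What the follow-up sentence covers.** The heading puts the word for seriousness in brackets, a device section 6.2 uses elsewhere to mean both kinds of event. The sentence below it therefore answers for serious and non-serious events. The reason it gives mentions serious events only. Non-serious events lose follow-up with no reason stated.

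**2. Whether the reason is enough for serious events.** The same section sets 24-hour and 15-day reporting for serious events. Those rules exist because an event that is not expected can still occur. The same logic applies to follow-up: not expecting a serious event does not make a rule for handling one inapplicable.

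**3. Follow-up against causality grading.** The two highest causality grades rest in part on whether the event improved after the procedure was stopped, and the highest also on recurrence after rechallenge. Each is a statement about the event's course. A footnote limits the dechallenge criterion to reactions where it applies, but where it does apply it cannot be assessed without observing what happens next. Section 6.2 thus asks for a judgement and declares the observation behind it not applicable.

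**4. Expectation against foreseen reactions.** Soreness, redness and tingling after a session are unfavourable symptoms or findings that follow a trial procedure in time. They meet the definition in section 6.2 whether or not they are related to the procedure. Section 7.2 foresees them as possible; section 6.2 says no adverse events, serious or not, are expected. The conflict lies between section 7.2 and that expectation sentence. The follow-up sentence speaks only of serious events, and the mild reactions in section 7.2 do not contradict its literal wording.

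**5. What is recorded and what is not.**

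| Element | Provided for? | Where |
|---|---|---|
| Severity grade | Yes | Section 6.2 |
| Causality grade | Yes | Section 6.2 |
| Documentation and reporting of serious events | Yes | Section 6.2 |
| Reporting of adverse events on the CRF | Yes, as a monitoring check that refers back to the protocol | Section 9 |
| Course, outcome or resolution date | No provision found | – |

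Section 9 refers to the protocol for how events are reported. On follow-up, the protocol's answer is that it does not apply.

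**The case against.** The strongest reply is that this is a risk class A study in healthy volunteers, with no safety endpoint and only mild, transient reactions foreseen. Participants attend twice weekly and rate thermal sensation and comfort after every diathermy treatment and discomfort after every training session, so a reaction has regular chances to surface. Severity and causality are graded by two parties, serious events are documented, the monitor checks CRF reporting, an annual safety report is due, and section 6.1 commits the study to ICH-GCP. On this view one careless sentence needs tidying and nothing more.

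Much of this stands. A reader might infer that adverse events would go unrecorded altogether. The documents do not support that, because the provisions just listed exist. A reader might also take the lack of an adverse event row in Appendix 1, or of a field in section 8.2, as proof that the CRF has none. The CRF is not among the documents, section 9 places adverse events on it, and a schedule of planned assessments often omits unscheduled reporting.

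The reply does not remove the core. The session ratings do not record skin findings, duration or resolution. A general commitment to ICH-GCP does not cancel a specific sentence declaring follow-up inapplicable. Low risk is a good argument for a simple follow-up rule, but not for stating that none applies while the causality table depends on one.

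**Conclusion.** The point holds as an internal contradiction with a practical consequence. Follow-up of all adverse events is set aside on a reason limited to serious ones. That conflicts with the causality grading and serious event reporting in section 6.2, and the section's expectation of no events conflicts with section 7.2. As written, nothing requires an event's course or outcome to be recorded.

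Its size is qualitative. It touches safety documentation for every participant and leaves the primary analysis and sample size unaffected. The documents give no event rates. A confidence limit for zero events would reflect the small sample and would be the same after the correction, so it would not measure this defect.

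Two further inferences should be resisted. One is that skin reactions are the only harm that could differ between arms: the sham arm also has the device applied to the skin, and nothing rules out a difference in soreness. The other is that the trial could not support the description of diathermy as safe in section 7.2. That description is a prior risk statement resting on past use and certification, and the trial has no safety objective to test it.

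The conclusion assumes that the bracketed heading means both kinds of event, as it does elsewhere in section 6.2, and that no separate document supplies a follow-up rule.

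**What to change.** - In section 6.2, delete the statement that follow-up is not applicable. Replace it with a sentence that adverse events and serious adverse events reported on the CRF are carried to a documented outcome with its date.
- Reconcile the expectation sentence in section 6.2 and the opening of section 7.2 with the reactions section 7.2 foresees.
- Make the section 9 monitoring check point to the revised text in section 6.2.
- State in section 5.1 that adverse events will be listed by arm, with severity, causality and outcome.
- Optionally, add an adverse event line to the per-session CRF and to Appendix 1, if the CRF does not already carry one.

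The cost is wording changes, one listing and a little extra documentation when an event occurs. No new procedure or visit is needed. How an event should be managed clinically is left to the sponsor and investigator.

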6.4 Radiation

The radiofrequency electromagnetic field caused by the diathermy device induces 448kHz capacitive monopolar radiation. This electromagnetic energy generates heat by oscillation and friction of charged molecules (Guy et al., 1974). Ultrasound is using high-frequency sound waves and not ionizing radiation to capture images like X-ray imaging. Therefore, no hazardous radiation is used in this study.

6.5 Pregnancy

Pregnant or breastfeeding woman are excluded from participating in the study. A urine pregnancy test is given to the women together with the participant information. The negative test result must be presented on the first examination day. In the event of a positive test, women will be asked to report this by telephone and will not be included in the study.

No risks regarding contraception of any kind are to be expected; to date, no such risks are known for this procedure. Participants who become pregnant during the study must inform their investigator immediately and may not continue to participate in the study.

6.6 Amendments

Substantial changes to the study setup, organization, protocol and related study documents will be submitted to the Ethics Committee for approval prior to implementation.

Under emergency circumstances, deviations from the protocol to protect the rights, safety and well-being of human subjects will be documented and reported to the Ethics Committee as soon as possible.

6.7 Notification and reporting upon completion, discontinuation or interruption of the study

Upon regular study completion, the Ethics Committee is notified via BASEC within 90 days (ClinO, Art. 38).

The Sponsor-Investigator may terminate the study prematurely according to certain circumstances, e.g.

- Ethical concerns,
- Insufficient participant recruitment,
- When the safety of the participants is doubtful or at risk (e.g. when the benefit-risk assessment is no longer positive),
- Alterations in accepted clinical practice that make the continuation of the study unwise, or
- Early evidence of harm or benefit of the experimental intervention

Upon premature study termination or study interruption, the Ethics Committee is notified via BASEC within 15 days (ClinO, Art. 38).

A final report is submitted to the Ethics Committee via BASEC within a year after completion or discontinuation of the study, unless a longer period is specified in the protocol (ClinO, Art. 38).

6.8 Insurance

In the event of study-related damage or injuries, the liability of the institution Thim van der Laan AG provides compensation, except for claims that arise from misconduct or gross negligence.

7 FURTHER ASPECTS

7.1 Overall ethical considerations

The study is being carried out on healthy volunteers. However, ILEX machines are also designed to provide a safe way for people with back problems to exercise. Therefore, training experience with ILEX machines will help not only healthy people, but also patients with back problems. In addition, heat therapy has the potential to support hypertrophy in resistance training. The results from the diathermy therapy will provide guidance for patients who are unable to examine resistance training to voluntary fatigue. Future studies in patients are planned to investigate the effect of training and preheating in relation to back problems.

7.2 Risk-benefit assessment

There are no health risks associated with participating in this study. The ILEX machine is CE-certified and based on equipment that has already been tested. The product is used in accordance with the instructions for use. The training sessions take place at low load and with a slow increase in load, which means that there is a negligible risk of injury. It is possible that fatigue of the back muscles or slight muscle soreness limited to the back may occur as a result of the training.

The use of diathermy therapies has been common practice for two decades. Treatment with the diathermy device is safe and most people find it very pleasant. Very sensitive skin may experience temporary redness and/or tingling. The tecar device is CE-certified and is used in accordance with the instructions for use.

Participation in the study does not result in any direct benefits for the test person. Ideally, the test participants improve the strength of the back extension muscles. The results of the study will help future people with back pain to receive effective treatment.

8 QUALITY CONTROL AND DATA PROTECTION

8.1 Quality measures

For quality assurance the sponsor, the Ethics Committee or an independent trial monitor may visit the research sites. Direct access to the source data and all study related files is granted on such occasions. All involved parties keep the participant data strictly confidential.

8.2 Data recording and source data

For this study, all data will be reported in the paper CRF and translated into a Microsoft Excel file (Version 16.79 (2023), Microsoft Corporation, Redmond, Washington, USA). Maximum isometric force and ROM of the back extensor are both automatically saved in Microsoft Access (Version 6_4, Microsoft Corporation, Redmond, Washington, USA), translated to the CRF and exported to Microsoft Excel. The image of the M. erector spinae, generated through the ultrasound system Mylab2 (Esaote, Maastricht, Netherlands), is exported to the software HorosTM (Horos Project, Annapolis, MD, USA). The result of measuring the muscle thickness is reported on the CRF file and entered into Microsoft excel. Epidemiologic data, inclusion and exclusion criteria, measurements of the sit-and-reach test, Biering-Sørrensen test, ratings of perceived effort, discomfort, thermal sensation, and comfort, and details of each training session are recorded directly on the CRF and transferred to Microsoft Excel.

8.3 Confidentiality and coding

Trial and participant data will be handled with uttermost discretion and is only accessible to authorized personnel who require the data to fulfil their duties within the scope of the study. On

the CRFs and other study specific documents, participants are only identified by a unique participant number.

The generated data are coded by a unique participant number. The Excel file is stored in Microsoft Teams classic (version 1.6.00.29954, Microsoft Corporation, Redmond, Washington, USA), which is accessible by the team of the Rehabilitation and Exercise Science Laboratory RESlab in Landquart with a password. The participation identification list is stored separately in Microsoft Teams in a password-protected area accessible only to the principal investigator of the study. Printed documents (CRF) are stored in a separate lockable filing cabinet. Only the principal investigator has the key to this cabinet. An automatic back-up of the Microsoft team takes place every night.

8.4 Retention and destruction of study data and biological material

All study data are archived for 10 after study termination or premature termination of the study. The generated data are transferred to a password-protected archive in Microsoft teams accessible for the RESLab team. The participation identification list is stored separately in Microsoft Teams in a password-protected area accessible only to the principal investigator of the study. Printed documents are stored in a separate lockable filing cabinet, only accessible for the principal investigator.

9 MONITORING AND REGISTRATION

The monitoring will be done by [name] [name] from the institution THIM – Die internationale Hochschule für Physiotherapie, [name].

[name] will ensure that trial is conducted and documented properly by carrying out the following activities when relevant and necessary to the trial:

- Verifying that the investigator has adequate qualifications and resources and remain adequate throughout the trial period, that facilities, including laboratories, equipment and staff, are adequate to safety and properly conduct the trial and remain adequate throughout the trial period.
- Verifying for the study interventions:
 - o That the intervention conditions are acceptable.
 - o That the study interventions are supplied only to subjects who are eligible to receive it.
 - o That subjects are provided with necessary instructions on the study interventions.
- Verifying that the investigator follows the approved protocol and all approved amendments, if any.
- Verifying that written informed consent was obtained before each subject participation in the trial.
- Ensuring that the investigator and the investigator's trial staff are adequately informed about the trial.
- Verifying that the investigator is enrolling only eligible subjects.
- Reporting the subject recruitment rate.
- Verifying that the investigator provides all the required reports, notifications, applications, and submissions, and that these documents are accurate, complete, timely, legible, dated, and identify the trial.
- Adverse events, concomitant medications and intercurrent illnesses are reported in accordance with the protocol on the CRFs
- Visits that the subjects fail to make, tests that are not conducted and examinations that are not performed are clearly reported as such on the CRFs.
- All withdrawals and dropouts of enrolled subjects from the trial are reported and explained on the CRFs.

This study will be registered on the Swiss National Clinical Trial Portal.

